• To compare the effects of PIT versus TAU on key psychological measures: suicidal ideation, depression, hopelessness, self-esteem and wellbeing, on the level of harm resulting from self-harm incidents, on the frequency of self-harm thoughts, and on the participant's ACCT status at 8 weeks.

Outcome measures

Primary outcome

	IRAS No: 241606	
WORSHIP III		

The primary outcome is the total number of self-harm incidents in the 8-week period from baseline. We shall also be measuring the total number of self-harm incidents in the 12-weeks from baseline. All self-harm which takes place at a specific time point will count as one incident. For example, if someone cuts themselves on their neck and arm at the same time this will count as one incident; however, if they cut themselves at two different times, in the same day, this will count as two incidents e.g. when there is a gap of 30 minutes between incidents. This approach is consistent with the way incidents of self-harm are recorded on SystmOne and the prison self-harm records e.g. the self-harm incidents log/ACCT/NOMIS/F213.

The primary outcome will be a composite of self-harm incidents derived from self-report, medical databases (SystmOne) and prison databases or paper records (NOMIS; F213 forms, ACCT folders, self-harm incidents logs; daily officer's logs) checked for double entry. This approach was recommended in Borschmann et al (2017) who conclude that relying on one data source for self-harm incidents in incarcerated adults could substantially under-ascertain the actual number of events [23]. Self-harm acts will be recorded on the self-harm incidents logs (participants, prison and SystmOne) and then checked for double entry before they are entered into the CTU database. The date and time of each self-reported incident will be recorded to allow cross-checking with medical and prison records, which record self-harm incidents by date and time, to check for duplication.

Both the intervention group and the control group will be asked to complete a weekly self-harm incidents' log (participants) outlining the number of times they have self-harmed since the last entry. All participants (in control and intervention arm) will be able to self-complete the log, at the end of one week, or complete the log with a research assistant. We will explore with each prison recruiting trusted peers to assist with log completion if the women have low literacy.

Secondary outcomes

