Becks Scale for Suicide Ideation [24]: a 19-item instrument measuring intensity, duration and specificity of thoughts about committing suicide. The BSS has high internal consistency (0.89) and high inter-rater reliability (0.83) [24].

Becks Depression Inventory [25]: a 21-item scale measuring symptoms of depression. The BDI-II has high internal consistency and a retest reliability ranging from 0.73 to 0.96 [26].

Beck Hopelessness Scale [27]: a 20-item self-report inventory designed to measure three major aspects of hopelessness: feelings about future, loss of motivation and expectations. The BHS has high concurrent validity (.86) and high reliability ($\alpha = .91$) [27].

Rosenberg Self-Esteem Scale [28]: a 10-item Likert scale with items answered on a four-point scale – from strongly agree to strongly disagree. The scale measures self-esteem and has been used in prison research [29]. Internal consistency ranges from .77 to .88 and test-retest reliability ranges from .82 to .85 [29].

Warwick-Edinburgh Mental Well-Being Scale [30]: a 14-item scale of mental well-being covering subjective well-being and psychological functioning, in which all items are worded positively and address aspects of positive mental health. The WEMWBS has high internal consistency (α = .91) and test-retest reliability (0.83) [30].

ACCT: The Assessment, Care in Custody and Teamwork (ACCT) process is a prison-based system for self-harm monitoring and management. We will record whether the participant is taking part in the ACCT process at 8-weeks and at 12 weeks.

Exploratory outcomes

	IRAS No: 241606
WORSHIP III	

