Level of harm resulting from self-harm incidents: Following Hawton et al [1], the level of harm resulting from self-harm incidents will be measured as follows: incidents will be classified as resulting in a high level of harm when they involve loss of life, resuscitation in prison, an overnight stay in hospital, external hospitalisation on life support or a combination of these. A medium level of harm will be defined as external hospitalisation other than life support (NOT an overnight stay) and a low level of harm will be defined as any episode not needing resuscitation or external hospitalisation. The level of harm will be recorded by the individual on the self-harm incidents' log (participants), for non-fatal incidents, and cross referenced with data recorded in the self-harm incidents logs (prison and SystmOne). Any deaths will be reported in the self-harm incidents logs (prison and SystmOne). For each participant, we shall calculate an average level of harm across all incidents.

Self-harm thoughts: Self-harm thoughts will be measured in a weekly diary on a Likert Scale. Women will be asked to report how often they have had thoughts of self-harm since the due date for their last weekly diary (not at all; almost never; sometimes; almost always; all the time).

Objectives	Outcome Measures	Timepoint(s) of evaluation of this outcome measure (if applicable)
Primary Objective To compare the effect of modified PIT versus TAU on incidents of self-harm	Self-harm incidents (composite of self-report and prison/healthcare records)	8-week post baseline (primary outcome); 12-weeks post baseline
Secondary/Exploratory Objectives To compare the effects of PIT versus TAU on key psychological measures: suicidal ideation, depression, hopelessness, self-esteem and wellbeing, on the level of harm resulting from self-harm incidents, on the frequency of self-harm thoughts, and on the participant's ACCT status.	Becks Scale for Suicide Ideation Becks Depression Inventory Beck Hopelessness Scale Rosenberg Self-Esteem Scale Warwick-Edinburgh Mental Well-Being Scale Prison ACCT documents Self-reported self-harm thoughts Likert scale (in the diary) Self-reported level of harm resulting from self-harm incidents cross referenced with prison records and SystmOne	8-weeks post baseline; 12- weeks post baseline
Process Evaluation	Therapy Satisfaction Questionnaire	10 weeks post baseline

Table of outcomes.

TRIAL DESIGN

Pragmatic randomised controlled trial

	IRAS No: 241606	

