During the study period (12-weeks), all participants will complete a weekly diary and the Self-Harm Incidents' Log (Participants), alone, with a trusted peer, or with the research assistant. They will also complete the Concomitant Therapies Form with a research assistant. The diary will include any thoughts of self-harm that have occurred since the last diary date, and any life events which have influenced their self-harm (including the time spent outside their cell). The Self-Harm Incidents' Log (Participants) will include incidents of self-harm in the last week and the severity of the incidents of self-harm. The Concomitant Therapies Form will contain information on any new therapy that has been started during the study period. Information in the Self-Harm Incidents' Log (Participants), will be cross checked with information from prison records (e.g. self-harm incidents databases) and SystmOne using the relevant Self-Harm Incidents' Logs. Concomitant Medications will be recorded from SystmOne on the concomitant therapies this information will be checked using the relevant details for the concomitant therapies this information will be checked using the relevant prison or healthcare databases. We shall also collect the dates and duration of time that women spent on a basic regime during the intervention period from NOMIS on the Basic Regime Data Collection Form.

At 8-weeks and 12-weeks, all participants will complete the secondary outcome measures (BSS; BDI-II; BHS; RSE; WEMWBS) and the health related quality of life scales (EQ-5D-5L; SF-12) and we shall record on the ACCT Status Form whether or not they are participating in the ACCT process.

If a participant is transferred part way through the research, we will seek permission from the receiving prison to complete the ongoing measures (e.g. concomitant medication) and the follow up measures. This will require local access to prison and healthcare databases. We will seek permission from the

WORSHIP III	IRAS No: 241606

participant in the consent process to contact their probation office / CRC for help to locate the women to try to complete ongoing and follow up measures.

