An opportunity sample of 264 women will be recruited to the research. The sample size is powered to detect a minimal important clinical difference of 33% reduction in self-harm incidents over 8 weeks. This clinically significant difference is based on Hawton et al's systematic review of the efficacy of psychological and pharmacological interventions designed to reduce self-harm repetition [43]. From MOJ prison data, the average number of self-harm episodes over 8 weeks in the control group was 6.65 [3]. We modelled this with a Poisson distribution (mean and variance=6.65) and used Monte Carlo simulations with 1000 simulations to estimate the power for a range of sample sizes, with power defined as the proportion of estimated p-values less than 0.05 for null hypothesis testing (treatment effect is 0), against an alternative hypothesis (33% reduction in the log of the outcome). With 5% significance, to obtain 90% power, we will require 105 per group for the primary analyses. Based on WORSHIP II [6] we estimate 20% attrition so will recruit 132 per group at baseline. This level of attrition is not expected in the primary outcome, due to availability of prison data and the fact that self-reported incidents will be measured on a weekly basis, but allows for attrition in the secondary outcomes.

We expect that there will be several potential therapists because we are using trainees as well as qualified professionals. This means that each therapist will see a small number of participants each (mean≈6.6). In turn, we expect that the ICC will be small (though no estimates are available to inform our calculations), and since the number of participants per cluster is also small, the corresponding design effect indicates a small increase to the sample size would be required to take into account this clustering. We anticipate that this will be balanced by accounting for baseline prognostic factors in our statistical models, and that 90% power will be maintained with lower than 20% attrition rate for the primary outcome. We shall include a random effect for each therapist within the statistical analysis models.

Planned recruitment rate

The predicted figures have been calculated based on the number of women who will pass through each of the prisons, depending on their size and the recruitment rate achieved in WORSHIP II. The predicted figures (confirmed by HMPPS) are calculated as follows:

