Analyses of the quantitative data will use an intention-to-treat (ITT) approach with analysis of randomised participants, regardless of non-compliance with protocol. Analyses will post-date final follow-up assessments, with consideration of potential biases from loss to follow-up. The primary outcome (number of incidents of self-harm at 8 weeks) will be analysed using a mixed Poisson model that adjusts for pre-specified baseline covariates and includes a random effect for therapist (since there are multiple therapists per site).

Secondary outcomes will be analysed using a linear mixed model over all repeated measures. Time will be included as a categorical factor, as well as a time*treatment interaction. We will estimate the effect at 8 and 12 weeks separately and report these as an adjusted mean difference.

WORSHIP III	IRAS No: 241606

We can explore possible subgroup effects (particularly around ethnicity, see above) using a treatment by covariate interaction in the fixed part of the model. We are not powered to detect significant interactions and are not currently pre-specifying any potential subgroups.

As secondary analyses, we shall explore a dose-response relationship using randomisation as an instrumental variable for number of sessions received. If there are significant effects on secondary outcomes which are also potential mechanisms (e.g. hopelessness, self-esteem), we shall perform a mediation analysis to test if these account for any observed treatment effects on the primary outcome using causal mediation approaches.

The sensitivities of all treatment effect estimates to missing outcome data will be explored; these models will explore the robustness of the treatment estimates to whatever small amount of missing data there is. The main analysis will use all available data that we believe are valid under the assumption of missing at random. We shall then use a suite of sensitivity analysis to explore the robustness of the primary analysis to departures from assumptions, including all randomised participants. If required, sensitivity analyses will include multiple imputation, and imputing a range of values for missing data under missing not at random assumptions.

Qualitative Analysis

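### Mediation is run only for scales that reach significance in the same data, so reported indirect effects are biased away from zero when true scale effects are modest

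*Protocol*

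**What the plan says.** Under Statistics and Data Analysis, the statistical analysis plan section lists mediation among the secondary analyses and sets an entry condition: "If there are significant effects on secondary outcomes which are also potential mechanisms (e.g. hopelessness, self-esteem), we shall perform a mediation analysis". The rest of that sentence gives the purpose, namely "to test if these account for any observed treatment effects on the primary outcome using causal mediation approaches". Two conditions are thus built in. The scale must show a significant treatment effect, and there must be a treatment effect on the primary outcome to explain. Hopelessness and self-esteem are given only as examples.

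Trial Procedures gives the scales and times: "At 8-weeks and 12-weeks, all participants will complete the secondary outcome measures (BSS; BDI-II; BHS; RSE; WEMWBS". The analysis section adds: "We will estimate the effect at 8 and 12 weeks separately and report these as an adjusted mean difference". The rule does not say which time point decides. The secondary objective is worded for 8 weeks only ("on the frequency of self-harm thoughts, and on the participant's ACCT status at 8 weeks"), while the Table of outcomes lists "8-weeks post baseline; 12- weeks post baseline".

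A significance level appears only in the sample size calculation: "With 5% significance, to obtain 90% power, we will require 105 per group for the primary analyses". The protocol gives neither a level nor a multiplicity rule for the secondary scales, and it does not say that there is none.

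**The concern.** An indirect effect is the product of the treatment-to-mediator effect (*a*) and the mediator-to-outcome effect (*b*). The rule looks at the estimate of *a*, keeps the scale only if that estimate is large relative to its standard error, and then uses the same estimate in the product. Estimates kept in this way are too large on average unless nearly all of them would have been kept anyway. The sample size was set for the primary outcome, so modest scale effects, where the bias is greatest, cannot be ruled out.

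What is at stake is the size of any reported mechanism, and whether readers see results for every plausible mediator or only for those that passed.

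**Working it through.** The protocol states no error rate or bias for this step, so there is no figure of its own to reproduce.

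**Inputs**
- 105 per arm with scale data (sample size calculation; 132 × 0.80 = 105.6).
- Two-sided 5% level for the scales (assumed; stated only for the primary analysis).
- Correlation of 0.6 between baseline and follow-up score (assumed), giving a residual SD of √(1 − 0.6²) = 0.8.
- *b* = 0.4 in a linear outcome model (assumed). It cancels from the inflation ratio.
- Five scales (Trial Procedures), two of them named in the rule.

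**Step 1: the gate.** SE(*a*) = 0.8 × √(2/105) = 0.1104. A scale passes if its estimate exceeds 1.96 × 0.1104 = 0.216 SD in absolute value. A true effect below 0.216 SD can therefore be reported in the right direction only as an overestimate.

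**Step 2: size of the selected estimate.** With m = *a*/SE:
- P(pass) = Φ(m − 1.96) + Φ(−m − 1.96)
- E(estimate | pass) = *a* + SE × [φ(1.96 − m) − φ(1.96 + m)] / P(pass)

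At *a* = 0.2, m = 1.811 and P = Φ(−0.149) + Φ(−3.771) = 0.441. The conditional mean is 0.2 + 0.1104 × (0.3946 − 0.0003)/0.441 = 0.299, which is 1.49 times the truth.

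| True *a* (SD) | P(pass) | Mean estimate given pass | Ratio to truth |
|---|---|---|---|
| 0.1 | 0.148 | 0.266 | 2.66 |
| 0.2 | 0.441 | 0.299 | 1.49 |
| 0.3 | 0.776 | 0.343 | 1.14 |
| 0.4 | 0.952 | 0.412 | 1.03 |

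Simulating the full product (20,000 trials per setting) agrees. The mean selected indirect effect is 0.106 against a true 0.040, 0.119 against 0.080, 0.136 against 0.120, and 0.165 against 0.160. Without the gate the mean equals the truth and 95% CI coverage is about 0.95. If baseline explained nothing (residual SD 1.0), the ratios at 0.2, 0.3 and 0.4 SD would be 1.79, 1.31 and 1.11.

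**Step 3: false claims and power.** With *a* = 0, 5.1% of trials pass and 90.9% of those give an indirect-effect CI excluding zero: 0.051 × 0.909 = 4.6% of all trials, against 5.4% with no gate. A repeat run gave 5.4% against 5.5%. At a true 0.2 SD, the CI excludes zero in 42.5% of gated and 44.0% of ungated trials in one run, and in 41.4% either way in another. An indirect-effect CI seldom excludes zero unless *a* itself is significant, so the gate is nearly redundant as a test.

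**Step 4: chance that some scale passes when none is affected (8 weeks).** With independent tests:
- five scales: 1 − 0.95⁵ = 22.6%
- the two named scales: 1 − 0.95² = 9.8%

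By simulation with correlated scales, five give 18.3% at correlation 0.5 and 12.7% at 0.8; two give 7.8% at 0.8. The ranges are about 13-23% and 8-10%.

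**Step 5: adding the primary condition.** With no effect on anything and a significant primary result also required, five scales at mutual correlation 0.5 give 0.05 × 0.183 = 0.9% if the primary statistic is independent of the scales, and 2.6% by simulation if it correlates 0.5 with each. That is about 1-3%. If PIT truly reduces incidents but not through these scales, then at 90% primary power the chance that a scale passes, given a significant primary result, is 16-18% over the same correlations.

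**The case against.** The strongest defence is that the gate does little harm as a test. Several stronger readings are tempting, and the documents do not support them.

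- **That the gate manufactures mediators.** A reader might set the 91% of gated null analyses that look positive against about 5% ungated. That compares a conditional rate with an unconditional one. Over all trials the rates are practically equal (Step 3).
- **That true mediators are lost.** At 0.2 SD the analysis is skipped 56% of the time, but almost all the skipped analyses would have been inconclusive. What is lost is their estimates and intervals, with hardly any detections.
- **That ten unadjusted tests drive the selection.** Five scales at two times make ten tests, but a 12-week score cannot mediate a count that closes at week 8. The rule covers only potential mechanisms, and silence on adjustment does not mean there is none. The level and any multiplicity rule may properly sit in the statistical analysis plan, which is not at hand.
- **That this is the trial's formal test of how PIT works.** No mechanism objective is listed. The route hypothesised in the Rationale runs through self-harm thoughts, which is an exploratory outcome. The scale effects themselves are reported whatever their p-values.

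The link to an observed primary effect also protects when nothing works, though hardly at all when PIT works by another route (Step 5). What survives is the bias in the size of the reported indirect effects. The selection rule is written in the protocol, so this is more than detail left to a later document.

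**Conclusion.** The point holds, at minor severity. The rule selects on one factor of the quantity it then estimates, from an open list. The resulting bias is material if true scale effects are about 0.1 to 0.2 SD, moderate at 0.3 SD and negligible at 0.4 SD.

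These figures rest on 105 per arm, a two-sided 5% gate, an assumed baseline correlation of 0.6 and a linear product of coefficients. A log-link model for the count would change the scale of *b*, but not the selection on *a*. The chance-selection figures depend on assumed correlations and are ranges for that reason. False-positive mediation claims and power are essentially unchanged, and neither the primary analysis nor the reported secondary effects are touched.

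**What to change.** In the protocol's statistical analysis plan section, replace the significance condition with a short list of candidate mediators named in advance and measured at 8 weeks or earlier. Hopelessness and self-esteem at 8 weeks are the obvious entries. The team may also consider self-harm thoughts, which the weekly diary captures and the Rationale proposes as the route. Estimate the indirect effect for each named mediator whatever the p-value of its treatment effect, report all of them with 95% CIs, and label the analysis exploratory.

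The cost is a wording change and a few extra model runs on data already being collected, with no additional women or visits. The downside is that some intervals will be inconclusive and must be reported as such.

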Appendix 1 – Amendment History

	IRAS No: 241606	
WORSHIP III		

 transferred. We adjusted the recruitment targets in the protocol to reflect these changes. We also changed one of the main study prisons to HMP Eastwood Park rather than HMP Drake Hall as this prison has the largest self-harm rate nationally. We also added a sentence in the protocol to reflect the fact that the prison sites may change. We have requested permission to recruit in 9 prisons in case we encounter any recruitment problems at specific sites. The screening questionnaire was replaced by the eligibility form and reflects the revised inclusion/exclusion criteria. The wording of the inclusion and exclusion criteria was refined so that they result in clear yes/no answers on the CTU database. We also moved the inclusion or terber treatments to the exclusion to avoid the confusion of a double negative in the data collection forms. We specified that the participant needs to have 8-weeks left in the prison at baseline rather than screening and added that we need to check if participants are booked on clashing courses/treatments as well as currently taking them. We also specified in the protocol that therapies which overlap with the aims of PIT include therapies which are designed to affect the secondary outcomes e.g. Self-Esteem Courses. During CTU development, we edited questions on the bespoke baseline measures Demographic and personal history questionnaire: To aid data entry and following discussions during database development, we included detailed category options for ethnicity and marital status and additional possible locations for the women's children. We also moved the information on drug and alcohol use to a separate Alcohol and Drug History form. On the Mental Health History Coursionnaire we added extra categories for past diagnoses, refined the questions on past mental health admissions for clarity, included
Eastwood Park rather than HMP Drake Hall as this prison has the largest self-harm rate nationally. We also added a sentence in the protocol to reflect the fact that the prison sites may change. We have requested permission to recruit in 9 prisons in case we encounter any recruitment problems at specific sites. The screening questionnaire was replaced by the eligibility form and reflects the revised inclusion criteria was refined so that they result in clear yes/no answers on the CTU database. We also moved the inclusion criterion re other treatments to the exclusion to avoid the confusion of a double negative in the data collection forms. We specified that the participant needs to have 8-weeks left in the prison at baseline rather than screening and added that we need to check if participants are booked on clashing courses/treatments as well as currently taking them. We also specified in the protocol that therapies which overlap with the aims of PIT include therapies which are designed to affect the secondary outcomes e.g. Self- Esteem Courses. During CTU development, we edited questions on the bespoke baseline measures Demographic and personal history questionnaire: To aid data entry and following discussions during database development, we included detailed category options for ethnicity and marital status and additional possible locations for the women's children. We also moved the information on drug and alcohol use to a separate Alcohol and Drug History form. On the Mental Health History Form. On the Mental Health History form and the self- harm information to the Mental Health History Form.
has the largest self-harm rate nationally. We also added a sentence in the protocol to reflect the fact that the prison sites may change. We have requested permission to recruit in 9 prisons in case we encounter any recruitment problems at specific sites. The screening questionnaire was replaced by the eligibility form and reflects the revised inclusion/exclusion criteria. The wording of the inclusion and exclusion criteria was refined so that they result in clear yes/no answers on the CTU database. We also moved the inclusion criterion re other treatments to the exclusion to avoid the confusion of a double negative in the data collection forms. We specified that the participant needs to have 8-weeks left in the prison at baseline rather than screening and added that we need to check if participants are booked on clashing courses/treatments as well as currently taking them. We also specified in the protocol that therapies which overlap with the aims of PIT include therapies which are designed to affect the secondary outcomes e.g. Self- Esteem Courses. During CTU development, we edited questions on the bespoke baseline measures Demographic and personal history questionnaire: To aid data entry and following discussions during database development, we included detailed category options for ethnicity and marital status and additional possible locations for the women's children. We also moved the information on drug and alcohol use to a separate Alcohol and Drug History form. On the Mental Health History form. On the Mental Health History form. On the Mental Health History form.
sentence in the protocol to reflect the fact that the prison sites may change. We have requested permission to recruit in 9 prisons in case we encounter any recruitment problems at specific sites. The screening questionnaire was replaced by the eligibility form and reflects the revised inclusion/exclusion criteria. The wording of the inclusion and exclusion criteria was refined so that they result in clear yes/no answers on the CTU database. We also moved the inclusion criterion re other treatments to the exclusion to avoid the confusion of a double negative in the data collection forms. We specified that the participant needs to have 8-weeks left in the prison at baseline rather than screening and added that we need to check if participants are booked on clashing courses/treatments as well as currently taking them. We also specified in the protocol that therapies which overlap with the aims of PIT include therapies which are designed to affect the secondary outcomes e.g. Self- Esteem Courses. During CTU development, we edited questions on the bespoke baseline measures Demographic and personal history questionnaire: To aid data entry and following discussions during database development, we included detailed category options for ethnicity and marital status and additional possible locations for the women's children. We also moved the information on drug and alcohol use to a separate Alcohol and Drug History form and the self- harm information to the Mental Health History Form. On the Mental Health History Form. On the Mental Health History form and the self- harm information to the Mental Health History Form.
recruit in 9 prisons in case we encounter any recruitment problems at specific sites. The screening questionnaire was replaced by the eligibility form and reflects the revised inclusion/exclusion criteria. The wording of the inclusion and exclusion criteria was refined so that they result in clear yes/no answers on the CTU database. We also moved the inclusion criterion re other treatments to the exclusion to avoid the confusion of a double negative in the data collection forms. We specified that the participant needs to have 8-weeks left in the prison at baseline rather than screening and added that we need to check if participants are booked on clashing courses/treatments as well as currently taking them. We also specified in the protocol that therapies which overlap with the aims of PIT include therapies which are designed to affect the secondary outcomes e.g. Self- Esteem Courses. During CTU development, we edited questions on the bespoke baseline measures Demographic and personal history questionnaire: To aid data entry and following discussions during database development, we included detailed category options for ethnicity and marital status and additional possible locations for the women's children. We also moved the information on drug and alcohol use to a separate Alcohol and Drug History form and the self- harm information to the Mental Health History Form. On the Mental Health History Questionnaire we added extra categories for past diagnoses, refined the questions on past mental health admissions for clarity, included
 problems at specific sites. The screening questionnaire was replaced by the eligibility form and reflects the revised inclusion/exclusion criteria. The wording of the inclusion and exclusion criteria was refined so that they result in clear yes/no answers on the CTU database. We also moved the inclusion criterion re other treatments to the exclusion to avoid the confusion of a double negative in the data collection forms. We specified that the participant needs to have 8-weeks left in the prison at baseline rather than screening and added that we need to check if participants are booked on clashing courses/treatments as well as currently taking them. We also specified in the protocol that therapies which overlap with the aims of PIT include therapies which are designed to affect the secondary outcomes e.g. Self-Esteem Courses. During CTU development, we edited questions on the bespoke baseline measures Demographic and personal history questionnaire: To aid data entry and following discussions during database development, we included detailed category options for ethnicity and marital status and additional possible locations for the women's children. We also moved the information on drug and alcohol use to a separate Alcohol and Drug History form. And the self-harm information to the Mental Health History Form. On the Mental Health History Guestionnaire we added extra categories for past diagnoses, refined the questions on past mental health admissions for clarity, included
The screening questionnaire was replaced by the eligibility form and reflects the revised inclusion/exclusion criteria. The wording of the inclusion and exclusion criteria was refined so that they result in clear yes/no answers on the CTU database. We also moved the inclusion criterion re other treatments to the exclusion to avoid the confusion of a double negative in the data collection forms. We specified that the participant needs to have 8-weeks left in the prison at baseline rather than screening and added that we need to check if participants are booked on clashing courses/treatments as well as currently taking them. We also specified in the protocol that therapies which overlap with the aims of PIT include therapies which are designed to affect the secondary outcomes e.g. Self- Esteem Courses. During CTU development, we edited questions on the bespoke baseline measures Demographic and personal history questionnaire: To aid data entry and following discussions during database development, we included detailed category options for ethnicity and marital status and additional possible locations for the women's children. We also moved the information on drug and alcohol use to a separate Alcohol and Drug History Form. On the Mental Health History Questionnaire we added extra categories for past diagnoses, refined the questions on past mental health admissions for clarity, included
form and reflects the revised inclusion/exclusion criteria. The wording of the inclusion and exclusion criteria was refined so that they result in clear yes/no answers on the CTU database. We also moved the inclusion criterion re other treatments to the exclusion to avoid the confusion of a double negative in the data collection forms. We specified that the participant needs to have 8-weeks left in the prison at baseline rather than screening and added that we need to check if participants are booked on clashing courses/treatments as well as currently taking them. We also specified in the protocol that therapies which are designed to affect the secondary outcomes e.g. Self- Esteem Courses. During CTU development, we edited questions on the bespoke baseline measures Demographic and personal history questionnaire: To aid data entry and following discussions during database development, we included detailed category options for ethnicity and marital status and additional possible locations for the women's children. We also moved the information on drug and alcohol use to a separate Alcohol and Drug History form and the self- harm information to the Mental Health History Form. On the Mental Health History Questionnaire we added extra categories for past diagnoses, refined the questions on past mental health admissions for clarity, included
The wording of the inclusion and exclusion criteria was refined so that they result in clear yes/no answers on the CTU database. We also moved the inclusion criterion re other treatments to the exclusion to avoid the confusion of a double negative in the data collection forms. We specified that the participant needs to have 8-weeks left in the prison at baseline rather than screening and added that we need to check if participants are booked on clashing courses/treatments as well as currently taking them. We also specified in the protocol that therapies which overlap with the aims of PIT include therapies which are designed to affect the secondary outcomes e.g. Self- Esteem Courses. During CTU development, we edited questions on the bespoke baseline measures Demographic and personal history questionnaire: To aid data entry and following discussions during database development, we included detailed category options for ethnicity and marital status and additional possible locations for the women's children. We also moved the information on drug and alcohol use to a separate Alcohol and Drug History Form. On the Mental Health History Questionnaire we added extra categories for past diagnoses, refined the questions on past mental health admissions for clarity, included
refined so that they result in clear yes/no answers on the CTU database. We also moved the inclusion criterion re other treatments to the exclusion to avoid the confusion of a double negative in the data collection forms. We specified that the participant needs to have 8-weeks left in the prison at baseline rather than screening and added that we need to check if participants are booked on clashing courses/treatments as well as currently taking them. We also specified in the protocol that therapies which overlap with the aims of PIT include therapies which are designed to affect the secondary outcomes e.g. Self- Esteem Courses. During CTU development, we edited questions on the bespoke baseline measures Demographic and personal history questionnaire: To aid data entry and following discussions during database development, we included detailed category options for ethnicity and marital status and additional possible locations for the women's children. We also moved the information on drug and alcohol use to a separate Alcohol and Drug History form and the self- harm information to the Mental Health History Questionnaire we added extra categories for past diagnoses, refined the questions on past mental health admissions for clarity, included
CTU database. We also moved the inclusion criterion re other treatments to the exclusion to avoid the confusion of a double negative in the data collection forms. We specified that the participant needs to have 8-weeks left in the prison at baseline rather than screening and added that we need to check if participants are booked on clashing courses/treatments as well as currently taking them. We also specified in the protocol that therapies which overlap with the aims of PIT include therapies which are designed to affect the secondary outcomes e.g. Self- Esteem Courses. During CTU development, we edited questions on the bespoke baseline measures Demographic and personal history questionnaire: To aid data entry and following discussions during database development, we included detailed category options for ethnicity and marital status and additional possible locations for the women's children. We also moved the information on drug and alcohol use to a separate Alcohol and Drug History form and the self- harm information to the Mental Health History Form. On the Mental Health History form.
